# Effects of caffeinated chewing gum on 400-meter performance and fatigue index of sprinters: a crossover trial

#### Document Date: May 23, 2024

#### **Project summary**

The purpose of this study was to investigate the effect of caffeinated chewing gum on 400-meter sprint performance. Methods: Eight trained sprinter were divided into caffeine Gum trial (CAF) and Placebo trial (PL) with a randomized, double-blind study design. The participants chewing either caffeine Gum (CAF trial, containing 3 mg/kg of caffeine) or Placebo Gum (PL) for 10 minutes. After rested for 15 minutes, the participants underwent a Running-Based Anaerobic Sprint Test. After a 30-minute break, a 400-meter sprint test was performed. The blood lactate concentration were collected before and after 400-meter sprint from finger. Saliva samples were predicted to be collected before chewing gum, before the RAST, and after a 400-meter sprint. Saliva samples will be analyzed for caffeine and  $\alpha$ -amylase concentrations in saliva.

## Introduction

Many athletes use caffeine (1, 3, 7-trimethylxanthine) as a nutritional supplement, which is widely available in everyday foods such as coffee, chocolate, tea, cola and energy drinks. Caffeine intake can reduce fatigue by inhibiting adenosine receptors, increase the ability of the sarcoplasmic reticulum to release calcium ions, maintain sodium-potassium ATPase activity, and increase glycolysis before exercise(1, 2), all of which are mechanisms that can significantly increase sprinting speed (3), repetitive sprinting ability, and maximal muscular strength and explosive power (4). These increases in physical performance may be effective in improving athletic performance. Previous studies have shown that a pre-exercise caffeine intake of 3-6 mg per kilogram of body weight can achieve the highest concentration in the bloodstream one hour after intake (5, 6), resulting in performance enhancement. However, caffeine is slowly absorbed in the gastrointestinal tract and may cause gastrointestinal discomfort or excessive fluid intake (8). Finding alternative forms of caffeine supplementation may reduce gastrointestinal discomfort.

Caffeine supplementation using caffeinated gum before exercise has been found to be absorbed through the oral mucosa at a faster rate than caffeine capsules (7). In a study by Morris et al. in 2019, test subjects chewed gum containing 100 mg of caffeine for 2, 5, and 10 minutes to observe their caffeine absorption rate and blood levels. The results showed that 85% of the caffeine was effectively absorbed after 5 minutes of chewing caffeinated gum, and after 10 minutes, the caffeine in the gum was almost completely absorbed. In terms of blood concentration, the highest concentration of caffeine (8) was observed after 15 minutes of chewing caffeine gum. In terms of exercise performance, chewing gum containing 100-300 mg of caffeine 5-15 minutes before exercise can effectively improve aerobic capacity, slow down the decline of sprinting speed, increase vertical jump height, and enhance the effect of explosive power (9, 10).

Caffeine supplementation has been shown to be effective in enhancing exercise performance; however, it remains unclear whether chewing caffeine has the same significant effect on 400-meter spirting. Therefore, the purpose of this study was to investigate the effect of caffeine chewing gum on 400-meter spirting exercise performance and fatigue index.

#### Methods

#### Design

This study used a randomization crossover design with double-blind experimental design. Participants will be divided into a caffeinated chewing gum trial (CAF) and a placebo trail (PL). The placebo trail (PL). After the first trial, the participants rested and recovered for 7-10 days before the next trial, which was expected to be completed within one month. During the trial period, all participants maintained their normal training status, with no changes in training or retraining menus, and no over-training or extra competitions.

#### Participants

In this study, 15-20 healthy adult male sprinters were recruited as participants. Inclusion criteria were: 1. 6 years of professional short sprinting training, 2. 6 months of ongoing training, and 3. 3 months of recovery from sports injuries such as strains and sprains. Exclusions: 1. Non-specialized sprinters. 2. has not trained regularly for the past 6 months. 3. has recovered from an athletic injury. 4. less than 3 months of recovery from a sports injury, or participants with epilepsy, hypertension, hyperlipidemia, heart disease, arthritis, osteoporosis, brain injury, or a history of caffeine allergy. According to the results of last year's National Academy of Sciences program, caffeinated gum was found to have an effect on the fatigue index of basketball players with Cohen's d = 1.00. The effect was measured using the G\*POWER statistical software, with the POWER value set to 0.8, it was found that eight participants were sufficient to explain the validity of the study data. In order to achieve a more precise POWER value, the number of participants in this study was set at 15-20. All participants were fully explained the experimental procedure and informed of the possible risks before the experiment. This study received approval from the Institutional Review

Board of Jen-Ai Hospital - Dali Branch (202300071B0). This study was conducted following the Declaration of Helsinki.

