# Statistical analysis

All data are presented as averages  $\pm$  standard deviations. The Shapiro–Wilk test was used to examine the normality of the data. The result of were analyzed through a paired sample t test. All data were calculated using SPSS (version 20, Chicago, IL, USA), and the significance level was  $\alpha < 0.05$ .

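### Eight participants give 68% power, not 80%, if the paired t test is two-sided and the quoted d is the standardised paired difference; the protocol states neither

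*Protocol*

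**What the plan says.** The sample-size reasoning is in the Participants section of the protocol. It has three parts.

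- The effect size comes from an earlier project: "caffeinated gum was found to have an effect on the fatigue index of basketball players with Cohen's d = 1.00".
- The result from G*Power: "with the POWER value set to 0.8, it was found that eight participants were sufficient to explain the validity of the study data".
- The size chosen: "In order to achieve a more precise POWER value, the number of participants in this study was set at 15-20".

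That paragraph gives no significance level, no test, no sidedness and no definition of d. The Statistical analysis section supplies a test, "The result of were analyzed through a paired sample t test", and a level of 0.05, again without sidedness. The Design section describes a crossover, so each athlete is his own control. The Project summary gives a different size: "Eight trained sprinter were divided into caffeine Gum trial (CAF) and Placebo trial (PL").

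**The concern.** The protocol makes one claim about power: eight participants suffice for 0.8 at d = 1.00. A crossover analysed by a paired t test at 0.05, with nothing said about direction, would normally be taken as two-sided. Under that test eight looks too few for d = 1.00.

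If so, the chance of missing the assumed effect with eight athletes is about 32% and not the 20% implied. The reader also cannot fall back on the larger size, because the reason given for 15-20 states neither a power nor a detectable effect. And eight is not clearly just a minimum that was set aside, since the Project summary uses it as the number studied.

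**Working it through.** **Inputs.** From Participants: d = 1.00, target power 0.80, stated n = 8, size set 15-20. From Statistical analysis: paired t test, level 0.05. Assumed, because the protocol does not say: two-sided test; d = dz, the mean paired difference divided by the SD of the paired differences.

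**Formula.** For n pairs the test statistic has a noncentral t distribution with n − 1 degrees of freedom and noncentrality dz × √n. Two-sided power is P(T > t₀.₉₇₅) + P(T < −t₀.₉₇₅). One-sided power is P(T > t₀.₉₅).

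**1. Reproducing the stated eight.** Three routes lead there.

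- One-sided 5% t test, dz = 1.00: n = 7 gives 75.4% and n = 8 gives 81.5%. Eight is exactly the minimum.
- Two-sided normal approximation: n = (1.960 + 0.842)² / 1.00² = 7.85, rounded up to 8. This replaces the t distribution by the normal, which is too optimistic with 7 degrees of freedom: nominal power at eight is 80.7%, against the exact figure in step 2.
- Two-sided t test with d on the between-athlete SD and a high enough between-session correlation (step 3).

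**2. Two-sided exact t test, dz = 1.00.** At n = 8 the noncentrality is √8 = 2.83; at n = 10 it is √10 = 3.16.

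| n | Two-sided power | One-sided power |
|---|---|---|
| 8 | 68.1% | 81.5% |
| 9 | 74.8% | 86.2% |
| 10 | 80.3% | 89.8% |
| 15 | 94.9% | 97.9% |
| 20 | 98.9% | 99.6% |

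Ten is the first size to reach 80% two-sided. At eight the type II error is 100 − 68.1 = 31.9%, and 80% power would need dz = 1.16.

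**3. If d is on the between-athlete SD.** With equal SDs in the two sessions and correlation r between them, dz = d / √(2(1 − r)). The protocol gives no r, so the values below are assumptions.

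| r | dz | Two-sided power at n = 8 | n for 80%, two-sided |
|---|---|---|---|
| 0 | 0.71 | 41% | 18 |
| 0.3 | 0.85 | 54% | 14 |
| 0.5 | 1.00 | 68% | 10 |
| 0.6 | 1.12 | 77% | 9 |
| 0.7 | 1.29 | 88% | 7 |

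Setting dz = 1.156, the value needed at n = 8, gives r = 1 − 1/(2 × 1.156²) = 0.63. At or above that correlation eight is enough two-sided; below it, it is not.

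**The case against.** The strongest reply is that nothing has been shown to be miscalculated. The paragraph with the power claim names only d, the power and the software; two-sidedness is the reader's convention. A one-sided 5% calculation returns eight exactly, and the Introduction does expect caffeine to help. Even two-sided, 68% depends on reading Cohen's d as dz, and with r of about 0.63 or more the claim is true as it stands. Finally, the Participants section does not adopt eight. It sets 15-20, where two-sided power at dz = 1.00 is 95-99%.

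Much of this stands. A reader might infer that the sentence is simply an arithmetic error; the protocol does not support that, because an undeclared but possible choice reproduces it. A reader might also infer that the trial is underpowered; that does not follow for 15-20 participants at dz = 1.00.

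What does not stand is the idea that nothing needs changing. The stated aim is to study the effect of the gum, with no direction given, and a one-sided test is a choice that has to be declared. If eight came from a one-sided calculation and the analysis is two-sided, the two do not match. Nor can the gap be left to a SAP that may exist, because the protocol itself makes the power claim.

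**Conclusion.** The point holds conditionally. If the paired t test is two-sided at 0.05 and d = 1.00 is dz, eight participants give 68% power and ten are needed, so the stated 0.8 is not met: about 12 percentage points of power, or two participants. Confidence depends on those two readings. The first is conventional where no one-sided test is declared; the second cannot be checked, because the protocol does not define d or give a correlation.

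Severity is minor. At 15-20 the shortfall disappears for dz = 1.00. If d is on the between-athlete SD, 15 still exceeds the 14 needed at r = 0.3, though not the 18 needed at r = 0. The shortfall would have practical weight only if eight athletes were studied. The Project summary suggests that and the Participants section contradicts it; the protocol does not settle which is meant.

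**What to change.** 1. State in Participants and in Statistical analysis that the calculation and the test are two-sided at 0.05.
2. Say which d the earlier study reported. If it used the between-athlete SD, convert it to dz with the between-session correlation from that study and recalculate.
3. If it is dz, replace the sentence on eight participants with: *For dz = 1.00 and a two-sided paired t test at 0.05, ten participants give 80% power (eight give 68%).*
4. Replace the reason given for 15-20 with the power at that size, on the same assumption: *15-20 participants with both sessions analysed give 95-99% power at dz = 1.00.*
5. Reconcile the eight sprinters of the Project summary with the 15-20 of Participants.

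The cost is a few sentences and a look at the earlier study's effect size. No extra participants are needed if 15-20 is the planned size. The power quoted for eight becomes less favourable.

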#### Protocol

#### Experimental procedure

All experiments were scheduled to start at 3:00 pm. Upon arrival at the stadium, participants were fitted with a heart rate monitor (RS800; Polar Electro Oy, Kempele, Finland) to record their quiet heart rate and heart rate variability. This heart rate meter has been found to have very good reliability in measuring heart rate variability during exercise (11). After the heart rate meter is attached, the saliva of the participant is collected and analyzed for biochemical parameters. At the same time, a fingertip blood sample was taken to analyze the blood lactate concentration in the quiet state. After a 10-minute rest period, the participant will start a dynamic warm-up and record the content of the warm-up, and use the same warm-up content in the next experiment. After the warm-up, participants chewed caffeine gum (4 mg/kg for 10 minutes each time) or placebo (regular gum for 10 minutes each time) and rested for 15 minutes after the chewing. Before and after the 400-meter test, saliva samples and fingertip blood were taken again for subsequent biochemical and blood lactate analyses. After completing the first experiment, we rested for 7 days and then proceeded to the second formal experiment. Both experiments were completed within one month.

#### Outcome measure

The countermovement jump test was performed using a jumping mat (Fusion Sport, Coopers Plains, QLD, Australia). The participant stands on the jumping mat and stays as still as possible, jumping with his hands on his hips without swinging. After hearing the tester's instruction, the participant quickly squatted down until the knees were bent at a ninety-degree angle, and then jumped vertically as quickly as possible, allowing the feet to return to the jumping mat at the same time as a cushion. A total of 3 jumps were performed and the average height was analyzed.

The anaerobic sprint test, which consists of six 35-m maximal effort sprints with a 10-second rest between sets, measures peak power, mean power, minimum power, and fatigue index. It has been shown to have adequate reliability (12). The first time gate was placed at the starting position and the second time gate was placed at the 35m end point, with a sufficient distance for a 10 second buffer. After the participants were familiarized with the test procedure, they could start to prepare for the test. When the participants is ready, he stays still and completes six 35-meter sprints at maximum effort, with a 10-second break between each sprint. The time of completion of each sprint was recorded for subsequent analysis.

The 400-meter segmented sprint test is conducted using a timing grating (Witty, Microgate, Bolzano, Italy), which is placed at the starting point, 100 meters, 200 meters, 300 meters and 400 meters.

#### Caffeine and placebo gum

The caffeinated chewing gum used in this study (Military Energy Gum, Arctic Mint flavor; Stay Alert, Chicago, USA) has been used in previous studies (13). Each piece of gum contains 100 mg of caffeine in approximately 5 g of gum. The placebo gum used was a commercially available blue mint gum. In order to provide 4 mg of caffeine per kilogram of body weight and to achieve a double-blind effect, all chewing gums will be mashed, ground, homogenized, and reshaped with 0.3 g of peppermint flavoring powder, and will be similar in color, appearance, taste, weight, and size. All chewing gums were prepared by specialized personnel and given to the on-site testers after numbering. After chewing the gum, a questionnaire was given to the subjects to

confirm whether they could tell the difference between the two chewing gums.

# Statistical analysis

All data are presented as averages  $\pm$  standard deviations. The Shapiro–Wilk test was used to examine the normality of the data. The result of were analyzed through a paired sample t test. All data were calculated using SPSS (version 20, Chicago, IL, USA), and the significance level was  $\alpha < 0.05$ .

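### The paired t test named for this two-period crossover has no period term, so a shared shift from visit 1 to visit 2 costs precision and, if the gum orders are unequal, moves the estimate

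*Protocol*

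**What the plan says.** The Design section sets the structure: "This study used a randomization crossover design with double-blind experimental design". Each participant has one caffeine and one placebo visit. On the interval between them, Design says "the participants rested and recovered for 7-10 days before the next trial", while Experimental procedure says "After completing the first experiment, we rested for 7 days and then proceeded to the second formal experiment". That difference needs reconciling but does not affect this point.

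The Statistical analysis section names one comparison: "The result of were analyzed through a paired sample t test". It has no period or sequence term. The significance level is 0.05, with sidedness not stated.

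Under Participants, "the number of participants in this study was set at 15-20"; the Project summary speaks of eight. The planning effect, Cohen's d = 1.00, comes from earlier work in which "caffeinated gum was found to have an effect on the fatigue index of basketball players". The Protocol does not say that the two gum orders will be equal in number, and the planned range includes odd totals, for which they cannot be.

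Several provisions should limit a change between visits: unchanged training (Design), a fixed start time and repeated warm-up (Experimental procedure), and, in the anaerobic sprint paragraph of Outcome measure, "After the participants were familiarized with the test procedure, they could start to prepare for the test". That section states no such familiarisation for the 400-metre test or the jump test.

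**The concern.** In a two-period crossover, everyone may do somewhat better or worse at the second visit, through learning, weather, fitness or motivation. A participant who takes placebo first has the shift added to the caffeine-minus-placebo difference; one who takes caffeine first has it subtracted. Pooling the differences in a paired t test ignores this known structure.

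There are two consequences. First, the spread between the two orders is counted as random error, so intervals widen and power falls. Second, if the orders are unequal, part of the shift stays in the mean difference and passes for a gum effect, in either direction. The randomised order needed to remove both is already part of the design, but the named analysis does not use it.

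**Working it through.** **The plan's own figure.** For a paired t test with d = 1.00 (read as mean over SD of the paired differences) and alpha 0.05, n = 8 gives one-sided power 0.815 and two-sided power 0.681. Two-sided 80% power needs n = 10 (0.803); the two-sided normal approximation gives 7.85, rounded up to 8. The stated eight is therefore reproduced one-sided or by the approximation. Everything below is two-sided.

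**Model.** For participant i, D = caffeine − placebo = τ + sπ + e. Here s = +1 if placebo comes first (n1 participants) and −1 if caffeine comes first (n2), π is the shared change from visit 1 to visit 2, and e has SD 1. The unit is therefore the SD of the paired difference with no shift. The size of π is an assumption, examined from 0 to 1.0.

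**Paired t test.**
- Expected estimate: τ + π(n1 − n2)/n.
- Expected sample variance of D: 1 + 4π²·n1·n2/[n(n − 1)].
- For 8:8 and π = 0.5: 1 + 4 × 0.25 × 64/240 = 1.267, so the SD is multiplied by √1.267 = 1.125.
- Bias at π = 0.5: 0.5 × 1/15 = 0.033 SD at a 7:8 split and 0.5 × 5/15 = 0.167 SD at 5:10.

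**With a period term.** The estimate is the average of the two order means. Its standard error is (s_p/2)·√(1/n1 + 1/n2), where s_p is the pooled within-order SD, on n − 2 degrees of freedom. π cancels.

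**Power at d = 1.00** (200,000 simulated trials per setting; paired t v with period term). At n = 15 a range covers the two directions of a 7:8 split.

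| Shift | n = 15 (7:8) | n = 20 (10:10) | n = 8 (4:4) |
|---|---|---|---|
| 0 | 0.949 v 0.946 | 0.988 v 0.988 | 0.681 v 0.656 |
| 0.25 | 0.933–0.948 v 0.945 | 0.986 v 0.988 | 0.656 v 0.657 |
| 0.5 | 0.895–0.931 v 0.945 | 0.978 v 0.989 | 0.578 v 0.655 |
| 1.0 | 0.696–0.834 v 0.945 | 0.917 v 0.988 | 0.336 v 0.657 |

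**A smaller effect**, chosen to give the paired test 80% power with no shift (not a Protocol figure), at shift 0.5:
- n = 15, effect 0.778: 0.681–0.760 v 0.794.
- n = 20, effect 0.66: 0.722 v 0.797.

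**Interval width.** Mean 95% half-width for 8:8 at shift 0.5 is 0.590 v 0.527, a ratio of 1.12, and the paired interval covers 0.970. At n = 16 and 20 the paired interval is wider by 3%, 12% and 43–44% at shifts 0.25, 0.5 and 1.0.

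**Type I error, near-equal orders.** The paired t test gives 0.044, 0.030 and 0.006–0.008 at shifts 0.25, 0.5 and 1.0. The period-adjusted test stays at about 0.050.

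**Unequal orders, n = 15 split 5 and 10, shift 0.5.** At effect 0.778 the paired power is 0.508 or 0.885, depending on which order is larger, against about 0.747 with the period term. Paired type I error is 0.062–0.063. If order were assigned by simple randomisation (assumed), a split of 5:10 or worse has probability 0.30. Averaged over such randomisation, the paired test's type I error is 0.050–0.051, so the bias is conditional on the split that occurs.

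**The case against.** The strongest reply is that this is a preference and not an error. The paired t test is valid with no shift, conservative with balanced orders, and holds its level on average over a randomised order. No passage gives a shift, and the setting argues for a small one: trained sprinters, unchanged training, a fixed hour, the same warm-up. At the Protocol's own d = 1.00 the gain is slight. At shift 0.25 it is 0.986 v 0.988 for n = 20, and even at shift 0.5 it is one point.

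Small shifts also favour the paired test. Because the period term costs a degree of freedom, with equal orders it gives narrower intervals only above a shift of about 0.25 SD at n = 8, or 0.08–0.11 SD at n = 16–20. With unequal orders, mean squared error improves only above √[n/(4·n1·n2)]: 0.26 SD at 7:8 and 0.27 SD at 5:10. For example, at 5:10 with shift 0.25 the paired estimate has 1/15 + 0.0625 × 25/225 = 0.0736, against 15/200 = 0.0750 with the period term.

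All of this stands, and it sets the weight of the point: a precision improvement, not a rescue. It does not reverse the recommendation. Near the break-even shifts the two methods differ in power by well under a point at n = 16–20, whereas at larger shifts the paired test loses several points. The planning effect is for the fatigue index in basketball players; the Protocol gives none for 400-metre time in sprinters, where a smaller effect would make the loss matter more. The named safeguards can shrink a shift but cannot remove it from the analysis.

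**Conclusion.** The point holds, as a change that should be made and not as a fatal flaw. The Protocol itself fixes a paired t test for a design in which order is randomised, and secures no balance of orders. If a shared shift between visits is present and not trivially small, intervals are too wide and power is lost. There is no excess of false positives unless the orders end up markedly unequal.

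The size depends on a shift the documents do not give, and on reading d = 1.00 as a paired effect. At an assumed 0.5 SD, the loss at d = 1.00 is about 1 point of power at n = 20, 1 to 5 points at n = 15, and about 8 points at n = 8. For an effect powered at 80% it is 3 to 11 points at n = 15 and about 7.5 at n = 20. Bias is 0.03 SD at 7:8 and 0.17 SD at 5:10, and can favour either gum.

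**What to change.** In Statistical analysis, replace the sentence naming the paired t test with:

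> Each outcome is analysed with participant, period and treatment terms (equivalently, a two-sample t test comparing the period differences between the two gum orders; the gum effect is half the difference in means), reported with its 95% confidence interval.

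In Design, state that the two gum orders are assigned equally, with an even number of participants. For lactate and saliva, which are sampled more than once per visit, say which value or change enters the analysis.

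The analysis change is wording only; in SPSS the two-sample form is an independent-samples t test. Equal assignment is a small change to the allocation list. If there is no shift, the price is one degree of freedom: under 1 point of power at n = 15–20 with near-equal orders, and about 2.5 points at n = 8 (0.681 to 0.656). At a 5:10 split it would be larger, 0.949 to 0.921 at d = 1.00 and 0.80 to 0.75 at effect 0.778; equal assignment avoids that cost.
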